# 5.5. Subject Withdrawal, Termination, and Replacement

Study subjects may discontinue from the study or be withdrawn from the study for any of the following reasons:

- At the subject's or the subject's legally authorized representative with the subject's assent request for any reason (withdrawal of consent)
- Subject whose cognitive function declines and is deemed by the Investigator to be unable to provide assent/consent for continuation in the study
- At the discretion of the Investigator, if deemed appropriate, for any reason
- At the discretion of the Sponsor, if deemed appropriate, for any reason
- Subject for whom investigator deems initiation of memantine medically necessary must be withdrawn
- Subject noncompliance: If a subject takes less than 70% of study drug tablets, this may be considered reason for withdrawal, by Investigator or Sponsor request
- Protocol violation that compromises subject safety
- For safety concerns; medically significant AE(s) or SAE(s) with CTCAE > Grade 3 may be considered reason for withdrawal, if appropriate in the judgment of the Investigator
- Subject who becomes pregnant must be withdrawn from the study
- The subject's caregiver/study partner is no longer willing or able to participate in the study and a suitable replacement caregiver/study partner cannot be found
- Brain MRI findings: subject who has any of the following findings on central reading:
  - o Macrohemorrhage: defined as hemorrhage with size > 1 cm^3
  - o ARIA-E (vasogenic edema) associated with neurologic symptoms: dosing will be halted for 1 month and MRI repeated. Resumption of dosing may be considered after discussion between Investigator and Sponsor's medical officer.
- Subject who experiences an event of syncope without a clear triggering event (e.g., blood draw or pain inducing a vasovagal episode) will be withdrawn from the study
- Subject with clinically notable ECG abnormalities based on the average of triplicate ECG readings. The criteria for clinically notable or significant ECG results that require subject withdrawal are as follows:
  - o QTcF (Fridericia's correction) interval > 500 msec, and
  - An increase in QTcF interval of > 60 msec from baseline.

Confidential Page 51 of 115

**Note:** The criteria for QTcF are based on the upper threshold in elderly subjects who are known to have higher ULN [Reardon & Malik, 1996], and is the threshold commonly used in AD studies.

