#### 7.1.10.7. Electrocardiogram

ECGs will be performed as shown in the Schedule of Assessments [Appendix 2]. A standard triplicate 12-lead ECG will be performed at the Screening – Part 2 Visit, Week 6, and Week 13. At subsequent visits, a single 12-lead ECG will be performed unless there is evidence of QT prolongation previously or in or current visit, in which case a triplicate ECG must be performed. The ECG should be obtained after the subject has rested in a supine position for at least 5 minutes. This assessment may be performed any time before blood sampling or at least 30 min after blood sampling, if applicable.

ECG intervals (e.g., interval representing the time for both ventricular depolarization and repolarization to occur [QT interval], QTcF interval, interval from the beginning of the Q wave to the termination of the S wave, representing the time for ventricular depolarization [QRS duration], and time from the onset of the P wave to the start of the QRS complex [PR interval]) and any clinically significant findings will be recorded. The tracings will be reviewed and reported by the central ECG reader.

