#### 7.2.8. Visit 7 – Week 26 (Day $183 \pm 14$ days)

The following procedures will be performed. The recommended order is shown below:

- Vital signs (prior to blood draw)
- Physical examination
- Neurological examination
- Weight

Confidential Page 72 of 115

- AE assessment
- Change in medications since last visit
- ADAS-Cog
- MMSE
- A-IADL
- CDR
- DAD
- NPI
- C-SSRS
- Single 12-lead ECG (triplicate if corrected QT [QTc] prolongation observed previously or in current visit)
- Safety laboratory tests
- Pre-dose plasma sample collection for biomarker assessment (exact time of sampling will be recorded)
- Pre-dose plasma sample collection for PK assessment (exact time will be recorded)
- Urine for urinalysis
- Urine pregnancy test (female subjects of childbearing potential)
- Study drug return, accountability, and compliance
- Study drug dosing (morning only). Exact times of dosing that occurred the night prior to clinic visit and during clinic visit will be recorded. The subject will be instructed not to take an evening dose on the day of the clinic visit.

- Study drug dispensing
- BP and pulse approximately 15 minutes after last blood draw
- MRI (within the visit window)

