#### 7.2.10. Visit 9 – Week 52 (Day $365 \pm 14$ days)

The following procedures will be performed. The recommended order is shown below:

- Vital signs (prior to blood draw)
- Physical examination
- Neurological examination
- Weight
- AE assessment
- Change in medications since last visit
- ADAS-Cog
- MMSE
- A-IADL
- CDR
- DAD
- NPI
- QoL-AD
- RUD Lite
- C-SSRS

Confidential Page 74 of 115

- Single 12-lead ECG (triplicate if QTc prolongation observed previously or in current visit)
- Safety laboratory tests
- Pre-dose plasma sample collection for biomarker assessment (exact time of sampling will be recorded)
- Pre-dose plasma sample collection for PK assessment (exact time will be recorded)
- Urine for urinalysis
- Urine pregnancy test (female subjects of childbearing potential)
- Study drug return, accountability, and compliance
- Study drug dosing (morning only). Exact times of dosing that occurred the night prior to clinic visit and during clinic visit will be recorded. The subject will be instructed not to take an evening dose on the day of the clinic visit.

- Study drug dispensing
- BP and pulse approximately 15 minutes after last blood draw
- MRI (within the visit window)

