### 7.2.12. Visit $11 - \text{Week } 78 \text{ (Day } 547 \pm 14 \text{ days)}$ [End of Treatment]

Week 78 visit is considered the end of treatment (EOT) visit. The following procedures will be performed. The recommended order is shown below:

- Vital signs (prior to blood draw)
- Physical examination
- Neurological examination
- Weight
- AE assessment
- Change in medications since last visit
- ADAS-Cog
- MMSE
- A-IADL
- CDR
- DAD
- NPI
- QoL-AD
- RUD Lite
- C-SSRS
- Single 12-lead ECG (triplicate if QTc prolongation observed previously or in current visit)

Confidential Page 76 of 115

- Safety laboratory tests
- Pre-dose plasma sample collection for biomarker assessment (exact time of sampling will be recorded)
- Pre-dose plasma sample collection for PK assessment (exact time will be recorded)
- Urine for urinalysis
- Urine pregnancy test (female subjects of childbearing potential)
- Study drug return, accountability, and compliance
- Study drug dosing (morning only). Exact times of dosing that occurred the night prior to clinic visit and during clinic visit will be recorded. The subject will be instructed not to take an evening dose on the day of the clinic visit.

- BP and pulse approximately 15 minutes after last blood draw
- MRI (within the visit window)I

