- 2. Vital sign measurements (BP, pulse, respiratory rate, and body temperature) will occur prior to dosing, LP, and blood draw, where applicable. BP and pulse will be measured after the subject has been sitting for 5 minutes. All BP measurements should be performed on the same arm, preferably by the same person, using an inflatable cuff and calibrated manometer. After last blood collections, subjects will be observed for approximately 15 minutes. BP and pulse while sitting will be measured and documented at the end of this observation period.
- 3. ECGs should be obtained after the subject has rested quietly in the supine position for at least 5 minutes. Triplicate ECG will be performed at screening, Week 6, and Week 13. Triplicate ECG at Week 26, Week 52, Week 78, and ET will be performed only if QTc prolongation observed in current and prior visits.
- 4. Lab tests include clinical chemistry, hematology, and coagulation tests, and will be done after ADAS-Cog and CDR-SB assessments.

Confidential Page 114 of 115

- 5. Serum FSH levels will be measured only for female subjects of non-childbearing potential. Serum hCG levels will be measured only for female subjects of childbearing potential.
- 6. Urine pregnancy tests will be conducted only for female subjects of childbearing potential.
- 7. For those who cannot undergo MRI, CT is acceptable at Screening but requires prior approval by Medical Monitor. These subjects will not be scheduled for further CT imaging and will not contribute to the assessment of the volumetric imaging biomarkers. Note: CT is not allowed for subjects of sites at Germany.
- 8. At screening, CDR global score and memory box score are calculated for screening purposes; the sum of boxes score is recorded at subsequent visits.
- 9. C-SSRS: B/S = baseline/screening version, SLV = since last visit version.
- 10. This CSF sub-study intends to enroll 60 subjects per treatment group. For each subject, LP will be performed within the same 2-hour window on each of the 3 visits regardless of dosing time and other assessments. In other words, for any two of the three CSF collections, the maximal time difference, in terms of the time of day, is within 2 hours from each other. Time of CSF collection (not time of preparation) will be recorded.
- 11. Plasma PK samples will be collected at pre-dose at each clinic visit. Additional, a PK sample at ≥ 1 hour post-dose during clinic visit will be collected at Week 65.

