8.5.5 Evaluation of Electrocardiogram (ECG) Findings

Electrocardiogram (ECG) Findings

Electrocardiograms will be assessed by a central reader and will be recorded at the following visits:

- Screening/Visit 1
- Visit 4/Day 43
- Visit 5/Day 92

- Visit 7/Week 26
- Visit 9/Week 52
- Visit 11/Week 78

The following quantitative parameters will be reported by the central reader: heart rate, PR interval, QRS duration, QT interval (uncorrected), and QT interval with Fridericia's correction (QTcF). Change from baseline and percent change from baseline by visits will be calculated for each parameter. The number and percent of patients within each category (normal, abnormal not clinically significant, and abnormal clinically significant) will also be summarized by visit. A standard triplicate 12-lead ECG will be performed at the Screening, Visit 4 and Visit 5. At subsequent visits, a single 12-lead ECG will be performed unless there is evidence of QT prolongation, in which case a triplicate ECG must be performed. Assessment of clinically notable abnormalities will be based on the average of triplicate ECG readings. To be conservative, the worst interpretation of the three readings will be used to generate the summary of ECG clinically notable abnormalities table. The denominator for the percentages will be the number of patients with a result at the specific visits for each parameter.

Clinically notable changes in ECGs will be listed for individual study subjects and tabular summaries provided per visit. The criteria for clinically significant ECGs results are as follows:

- PR interval \geq 220 msec
- PR interval ≤ 120 msec
- QRS duration ≥ 120 msec and increase of ≥ 20 msec from baseline
- OT interval >500 msec
- QTcF interval > 500 msec and increase of ≥ 60 msec from baseline

Categorical Analyses of QTcF Interval

At each visit with ECG, observed QTcF data will be summarized into the following categories and shift tables provided:

- Categories of QTcF \leq 450msec, 451-480 msec, 481-500 msec, and \geq 500 msec
- Categories of QTcF > 450 msec, > 480 msec, and > 500 msec
- Categories of CBL in QTcF: ≤ 10 msec, 11-30 msec, 31-60 msec
- Categories of CBL in QTcF: > 30 msec, > 60 msec

Vital Signs

Vital signs will be assessed at all visits except Visit 3 and Visit 6. The following parameters will be summarized: systolic blood pressure (SBP), diastolic blood pressure (DBP), body

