- 3. ECGs should be obtained after the subject has rested quietly in the supine position for at least 5 minutes. Triplicate ECG will be performed at screening, Week 6, and Week 13. Triplicate ECG at Week 26, Week 78, and ET will be performed only if QTc prolongation observed in current and prior visits.
- 4. Lab tests include clinical chemistry, hematology, and coagulation tests, and will be done after ADAS-Cog and CDR-SB assessments.
- 5. Serum FSH levels will be measured only for female subjects of non-childbearing potential. Serum hCG levels will be measured only for female subjects of childbearing potential.
- 6. Urine pregnancy tests will be conducted only for female subjects of childbearing potential.
- 7. For those who cannot undergo MRI, CT is acceptable at Screening but requires prior approval by Medical Monitor. These subjects will not be scheduled for further CT imaging and will not contribute to the assessment of the volumetric imaging biomarkers. Note: CT is not allowed for subjects of sites at Germany.
- 8. At screening, CDR global score and memory box score are calculated for screening purposes; the sum of boxes score is recorded at subsequent visits.
- 9. C-SSRS: B/S = baseline/screening version, SLV = since last visit version.
- 10. This CSF sub-study intends to enroll 60 subjects per treatment group. For each subject, LP will be performed within the same 2-hour window on each of the 3 visits regardless of dosing time and other assessments. In other words, for any two of the three CSF collections, the maximal time difference, in terms of the time of day, is within 2 hours from each other. Time of CSF collection (not time of preparation) will be recorded.
- 11. Plasma PK samples will be collected at pre-dose at each clinic visit. Additional, a PK sample at ≥ 1 hour post-dose during clinic visit will be collected at Week 65.
- 12. The times of study drug administration when taken at the study site will be recorded.
- 13. Last study drug administration will occur on the morning of the Week 78 visit. One dose is administered at the site during clinic visits; the evening dose is skipped on clinic visit days. #Baseline MMSE used for change from baseline analyses will be the average of V1a and V2 scores.

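### The footnote to the Protocol's schedule sets a stricter trigger for a triplicate ECG (prolongation at the current and prior visits) than Section 7.1.10.7 and the four visit lists (either one suffices)

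*Protocol*

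**What the plan says.** The trigger for a triplicate ECG after Week 13 is stated in several places.

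- Protocol Appendix 2, footnote 3: "Triplicate ECG at Week 26, Week 52, Week 78, and ET will be performed only if QTc prolongation observed in current and prior visits".
- Protocol Section 7.1.10.7 calls for a single 12-lead ECG at visits after Week 13 "unless there is evidence of QT prolongation previously or in or current visit, in which case a triplicate ECG must be performed".
- Protocol Section 7.2.8 (Week 26): "triplicate if corrected QT [QTc] prolongation observed previously or in current visit".
- Protocol Section 7.2.10 (Week 52): "triplicate if QTc prolongation observed previously or in current visit".
- Protocol Section 7.2.12 (Week 78): "Single 12-lead ECG (triplicate if QTc prolongation observed previously or in current visit". The Early Termination list in Section 7.2.14 has the same condition.
- SAP Section 8.5.5 calls for a single ECG "unless there is evidence of QT prolongation, in which case a triplicate ECG must be performed". It does not say at which visit the evidence must arise.
- SAP Appendix 1, footnote 3, a copy of the protocol schedule: "Triplicate ECG at Week 26, Week 78, and ET will be performed only if QTc prolongation observed in current and prior visits". Week 52 is missing from this sentence, although the SAP's own grid marks an ECG at that visit.

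Two rules use the result. Protocol Section 5.5 lists for withdrawal a "Subject with clinically notable ECG abnormalities based on the average of triplicate ECG readings", with QTcF above 500 msec and a rise of more than 60 msec from baseline. Protocol Section 10.10.5 also bases the assessment of notable ECG abnormalities on the triplicate average.

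**The concern.** The footnote joins the two conditions with *and* under an *only if*. The body of the protocol joins them with *or* and makes the triplicate mandatory. Both texts are current, and the SAP's copy carries the same *and*, so this is not a fault of text extraction.

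A site has reason to work from the Schedule. Section 7.1 says procedures follow it, and Sections 7.1.10.7 and 7.2 point to it as well. I found nothing in the protocol that says which text prevails when they differ.

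What is at stake is a subject-level safety decision. If prolongation first appears at Week 26 or Week 52 and the site follows the footnote, there is one tracing and no triplicate average. The withdrawal criterion in Section 5.5 cannot then be applied as written at that visit, and the subject remains on treatment.

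**Working it through.** No figure in the plan is in dispute, so the check is one of logic. Write P for prolongation seen at a prior visit and C for prolongation seen at the current visit.

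- Body-text rule (Protocol 7.1.10.7, 7.2.8, 7.2.10, 7.2.12, 7.2.14): triplicate if P or C.
- Footnote rule (Protocol Appendix 2, footnote 3, read literally): triplicate only if P and C.

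| Prior (P) | Current (C) | Body text | Footnote |
|---|---|---|---|
| no | no | single | single |
| no | yes | triplicate | single |
| yes | no | triplicate | single |
| yes | yes | triplicate | triplicate |

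The rules disagree in two of the four cells, and the two do not matter equally.

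1. *Prior no, current yes.* This is a first prolongation. The current reading may bear on the QTcF limit in Section 5.5, and the footnote leaves no triplicate to average. This is the cell that matters.
2. *Prior yes, current no.* The current tracing is not prolonged, so a missing triplicate has little bearing on a criterion that needs QTcF above 500 msec. The texts conflict here, but with little consequence for withdrawal.

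Next, the visits at which the first cell can affect withdrawal:

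- Screening, Week 6 and Week 13: triplicates are unconditional under both texts. No conflict.
- Week 26 and Week 52: conditional, with dosing continuing afterwards. The conflict can affect a withdrawal decision.
- Week 78: the last dose is given at this visit, so the withdrawal rule has nothing left to stop.
- Early Termination: the subject is already stopping.

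The effect on withdrawal is therefore confined to a first prolongation at Week 26 or Week 52.

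Last, whether the footnote changes how often ECGs are scheduled. After Week 13 they fall on Days 183, 365 and 547. The gaps are 365 − 183 = 182 days and 547 − 365 = 182 days under either rule. The footnote alters the number of tracings at a visit, not the time to the next one.

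**The case against.** The best case for leaving this alone is that the instruction is already clear. Section 7.1.10.7 points to the Schedule but then states the rule itself, in mandatory terms and with *or*. The four visit lists repeat it beside the ECG item. A site would have to pass over five statements to act on the footnote. The footnote can also be read loosely, as naming the set of visits to look through for prolongation. That reading is possible, but *only if* followed by *current and prior visits* more naturally requires both. If the loose reading is what was meant, the correction merely states it.

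The practical safeguards are also real. The single tracing is still read centrally (Section 7.1.10.7). The investigator or sponsor may withdraw a subject at discretion (Section 5.5). Unscheduled visits are allowed at any time (Section 7.2.16). The Safety Management Committee reviews ECG data at least monthly (Section 8.5). Nothing forbids a site from repeating an ECG. These points stand, and they keep the matter minor. They do not reconcile the two texts.

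A reader might go further and infer that the footnote opens a six-month gap in QTc surveillance. The documents do not support that: the 182 days come from the visit schedule and would be the same after the correction. Nor should two discordant cells out of four be read as a frequency. They are logical combinations, and only one bears on withdrawal.

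The SAP's copy has no operational force. It reproduces the protocol schedule, does not instruct sites, and was written after enrolment closed at 325 randomised subjects (SAP Section 4.1). SAP Section 8.5.5 does not require prolongation at both visits, but it does not say *or* either, so it is weak evidence for the intended rule.

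**Conclusion.** The inconsistency is real and minor. Read literally, Protocol Appendix 2 footnote 3 contradicts Section 7.1.10.7 and all four affected visit lists. At a first prolongation at Week 26 or Week 52 it would leave the Section 5.5 withdrawal rule and the Section 10.10.5 assessment without the triplicate average they call for.

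This rests on two assumptions: that the footnote is read literally, and that a site acts on it in preference to the body text. No number of affected subjects can be given, because the documents state no rate of QTc prolongation. The point concerns a safety procedure. It has no effect on efficacy, and the documents give no basis for inferring a difference between arms.

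**What to change.** In Protocol Appendix 2, footnote 3, replace *current and prior visits* with *the current or any prior visit*. For consistency, make the same replacement in SAP Appendix 1, footnote 3, and restore Week 52 to its list of visits. The SAP edit tidies the record and does not change which ECGs are taken.

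The cost is one phrase in each of two footnotes, plus the missing visit in the SAP copy. No visit or procedure is added beyond what Section 7.1.10.7 already requires. With enrolment complete, the change may come too late for some Week 26 and Week 52 visits. A short clarification to sites would cover those still to come.

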BID	Twice per day
BMI	Body mass index
BP	Blood pressure
C-SSRS	Columbia-Suicide Severity Rating Scale
CBL	Change from baseline
CDR	Clinical Dementia Rating
CDR-SB	Clinical Dementia Rating- Sum of Boxes
CDR-G	Clinical Dementia Rating- Global Score
СР	Completer population
CSF	Cerebrospinal fluid
CT	Computed tomography
DAD	Disability Assessment for Dementia
DSMB	Data and Safety Monitoring Board
ECG	Electrocardiogram
EOS	End of study
EOT	End of treatment
ET	Early termination
FSH	Follicle-stimulating hormone
GFAP	Glial fibrillary acidic protein
hCG	human chorionic gonadotropin
HCV RNA	Hepatitis C virus RNA
	Hepatitis B surface antigen
Hep B S Ag Hep C Ab	Hepatitis C antibody
TIEP C AU	ricpanus C annoug

1 INTRODUCTION

This document provides a detailed description of the statistical methods and procedures to be implemented during the analysis of Study ALZ-801-AD301 (APOLLOE4). The proposed methods and approaches describe the main planned data analyses. If the data suggest that alternate methods may be more appropriate, then deviations from this plan will be considered. However, any deviations from this Statistical Analysis Plan (SAP) must be substantiated by sound statistical rationale and documented in the final clinical study report.

2 STUDY OBJECTIVES

The objective of this Phase 3 study is to prospectively evaluate clinical efficacy and the long-term safety and tolerability of ALZ-801 over 78 weeks of treatment compared to placebo. The study will also evaluate volumetric imaging endpoints, and fluid biomarker effects of oral ALZ-801 over 78 weeks of treatment as exploratory outcomes.

